### **BACKGROUND:**

About one-third of adults in the US get insufficient sleep ( $\leq 6$  h per night; 7 h recommended) (1). Habitual sleep deprivation has been associated with adiposity and obesity in both clinical and epidemiological studies (2, 3). A primary reason for weight gain with inadequate sleep is excessive consumption of calories beyond the homeostatic energy requirement (4). Specifically, experimentally induced sleep deprivation increases the desire for foods high in sugar and fat content (5-7), and is related to excessive consumption of calories, especially from energy dense snacks (8, 9). A decline in sleep, paralleled by a steep rise in obesity rates has made it critical to understand the mechanistic link between chronic sleep deprivation and weight gain.

[figure not shown]
Sleep-deprivation has been shown to alter appetite-regulating hormones in humans (10, 11). In particular, sleep deprivation is associated with an increased availability of orexigenic hormones, such as ghrelin (10) and the *endocannabinoids* (2-arachidonoylglycerol (2-AG) and 2-oleoylglycerol (2-OG)) (11). However, how these hormonal alterations affect central processing of food stimuli, and how they result in enhanced food intake with sleep debt is not well understood in humans. Interestingly, studies suggest that orexigenic hormones may regulate appetite and food intake by altering olfactory sensitivity (12-14), hence leading to increased perception and intake of food (15). This would suggest that early olfactory cortices are among the first stages in the neural processing hierarchy at which sleep deprivation alters processing of food-related stimuli.

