## STUDY ENDPOINTS:

### Primary endpoints

The primary endpoints of this proposal are the analysis of neural representations of high-caloric food odors in early olfactory cortex and food reward regions, and levels of orexigenic hormones using the serial blood samples.

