### Secondary endpoints

Secondary endpoints of this proposal are the total calories of food consumed during the ad-libitum food intake phase, subjective ratings of hunger, fullness, prospective food consumption, and satiety using the visual analogue scale, food craving questionnaire, and total calorie intake using the self-reported food intake for 24 h following the fMRI scan.

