## PROCEDURES INVOLVED:

We propose to implement a randomized within-subject, crossover partial sleep-deprivation protocol to examine the effects of sleep deprivation (SD) on neural processing of food odors in early sensory and reward-related brain regions. In brief, after a one-week sleep stabilization period, subjects will spend a night either sleep deprived (SD, 4 h of sleep) or with normal sleep (non-SD, NDS, 8 h of sleep) at home. On the next day, fMRI scanning will be conducted at 7 pm after dinner, when sleep-deprivation induced changes in hormonal levels are most prominent (11). Hormone levels will be monitored using serial blood sampling in response to a meal (dinner).

**Sleep-deprivation protocol.** Subjects (N=40) will be randomly assigned to either participate in the SD or the NSD condition first (**Fig. 2A**). Subjects will then undergo a sleep stabilization phase to stabilize circadian rhythms. During this week, subjects will be instructed to keep a regular sleep schedule of 7-9 hours in bed between 10:30 pm and 7:30 am. Participants will abstain from alcohol, caffeine, and drugs in this phase. After the sleep stabilization week, the night before the fMRI session, subjects will either sleep normally (NSD, 8 h of sleep between 11 pm and 7 am), or sleep only for 4 h between 1 am and 5 am (SD) at home. We opted for a partial sleep-deprivation protocol because this situation (late bedtime and early wakeup) is ecologically valid as it reflects the most realistic form of sleep-deprivation in

everyday life. All subjects will participate in both sleep conditions (SD and NSD) in randomized order, separated by a 2.5-week washout period.

*Sleep-monitoring.* To ensure that subjects follow the sleep schedule during the sleep stabilization phase and sleep manipulation days, we will record sleep duration, as well as sleep and wake-up time using a daily sleep diary and wrist actigraphy (ActiGraph, LLC, Pensacola, Florida (45)). Additionally, subjects will rate their subjective sleep quality, alertness, and restfulness every morning using an online questionnaire. Subjects will also rate their subjective sleepiness using the Stanford Sleepiness Scale (46) before the fMRI scan during both the SD and NSD phase. Participants will spend the night of sleep manipulation (both SD and NSD) at home and food will be provided for these days.

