*Hormone levels.* As soon as subjects arrive at the imaging center, an intravenous sterile heparin-lock catheter will be inserted in a forearm vein and blood sampling will be initiated by the CRU mobile nurse. We will draw blood every 30 min after arrival, resulting in 5 samples, including a fasted baseline (6 pm), after dinner (6:30 pm), before (7 pm), during (7:30 pm, after the second scanning run), and after the scanning session (8 pm) for leptin and ghrelin analysis. An additional sample will be collected at 7:30 pm time point for 2-AG and 2-OG analysis. Plasma and serum samples will be frozen at  $-80^{\circ}\text{C}$  until assay for ghrelin, leptin, insulin using commercially available ELISA kits, and 2-AG and 2-OG using published procedures (49, 50). Phase of menstrual cycle in women has an impact on these hormonal levels. The 2.5-week washout period will ensure that the blood samples are collected in the same phase of the menstrual cycle

*Ad-libitum food intake.* At the completion of the fMRI scan, participants will be provided with snacks in a

buffet-style setting where they will have *ad libitum* access to food items corresponding to the odors used during fMRI scanning (sweet and savory high-calorie snacks). They will be instructed to consume as much food as they like. To measure food intake, food will be weighed pre- and post- consumption, and calories consumed will be calculated. Because subjects have been provided with dinner before the scanning session, food intake at the buffet will mainly reflect hedonic, rather than metabolic eating (47). *Appetite and hunger ratings.* Subjective food craving, ratings of hunger, fullness, prospective food consumption, and satiety will be measured using a visual analogue scale. These ratings will be acquired on the fMRI scanning day upon arrival, at all blood collection time points, and after the *ad libitum* meal. Subjects will also complete the food craving questionnaire on the day of fMRI scan.

*24 h post-fMRI food intake diary.* Subjects will be instructed to carefully record the food items, quantity consumed, place of consumption, and the food brands, for 24 h following the fMRI scan. We will calculate the total energy, fat and carbohydrate consumption for SD and NSD states.

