#### **DATA AND SPECIMEN MANAGEMENT:**

Sample size is based upon the requirements for group analysis, particularly when random-effects analyses are performed. Random-effects analyses require a minimum of 14 -18 subjects in each group in order to obtain statistically meaningful fMRI effects. Our target subject number also accounts for attrition in the subject pool due to unanticipated claustrophobia, technical/mechanical issues, or other problems during the fMRI session.

For the statistical analyses, comparisons of subjective appetite ratings and calorie intake between the SD and NSD state will be carried out using paired t-tests. Spearman's correlation analysis will be used to test the relation between appetite ratings, neural responses to food odors, and the total calories consumed. Moreover, we will use whole-brain mediation analysis (51) to identify the brain regions in which neural responses to food odors mediate the link between sleep-dependent changes in hormone levels and enhanced calorie intake. To identify brain mechanisms related to resilience, we will compare fMRI responses to food odors between subjects that manage to abstain from excess calorie intake in a sleep-deprived state to those that do not. We will use fMRI connectivity analyses (psychophysiological interaction, PPI (52)) to test the hypothesis that resilience to enhanced food intake in a SD state is associated with enhanced functional connectivity between the dorsolateral prefrontal cortex and reward-related brain regions (53). We will monitor sniffing using a breathing belt and spirometer, and model trial-by-trial sniff parameters will be included as covariates in all fMRI analyses following established procedures to control for respiration-induced effects.

To preserve subject privacy and confidentiality, all research materials (questionnaires, behavioral testing results, and magnetic resonance imaging data) will be coded by a different study code number unique for each subject, in order to keep the identity and personal information of each subject as confidential as possible. This number will be recorded on all testing sheets instead of the subject's

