### **Analysis of food intake**

Food items were weighed before and after eating to determine the amount of food consumed. Total calorie and energy density (kcal/g) of consumed food was calculated from the product nutrition labels. Changes in food intake in the deprived sleep (DS) session were computed as percentage change from non-sleep deprived baseline (NSD) and tested against zero using one-sample t-tests.

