### **Analysis of hormones**

Ghrelin, leptin, insulin, and cortisol were measured in blood samples collected at each session. Changes in hormone levels in the deprived sleep (DS) session were computed as percentage change from non-sleep deprived baseline (NSD) and tested against zero using one-sample t-tests.

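### Buffet intake and ghrelin are tested as percentage change from the NSD session against zero, a statistic with a positive mean when sleep has no effect

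*SAP*

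**What the plan says.** SAP, Analysis of food intake: changes in the deprived session (DS in the SAP, SD in the protocol) are "computed as percentage change from non-sleep deprived baseline (NSD) and tested against zero using one-sample t-tests". The quantities are total calories and energy density of the food eaten. SAP, Analysis of hormones, repeats the rule for ghrelin, leptin, insulin and cortisol: "Changes in hormone levels in the deprived sleep (DS) session were computed as percentage change".

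Protocol, Procedures Involved, describes the design: "All subjects will participate in both sleep conditions (SD and NSD) in randomized order". Protocol, Data and Specimen Management, plans a different scaling for intake: "comparisons of subjective appetite ratings and calorie intake between the SD and NSD state will be carried out using paired t-tests". It names no test for hormone levels.

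The outcomes at stake are a secondary endpoint, "total calories of food consumed during the ad-libitum food intake phase", and part of the primary endpoint, "levels of orexigenic hormones using the serial blood samples". Neither document gives a log scale, a rank test or a sensitivity analysis for these comparisons, or a rule for a subject who eats nothing at the NSD buffet.

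**The concern.** A one-sample t-test needs one value per subject, so the natural reading is 100 × (DS − NSD)/NSD for each subject, with the mean compared with zero. Zero is the right null value for a difference or a log ratio. It is not the right null value for this ratio when the denominator is as noisy as the numerator. Doubling counts as +100% and halving as −50%, so chance swings in opposite directions do not cancel.

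The lean is towards the hypothesis for two outcomes. Aim 2 of the protocol expects higher calorie intake after deprivation. The Background links deprivation to "increased availability of orexigenic hormones, such as ghrelin", and ghrelin is the only hormone in the SAP's list that the Background names as orexigenic. For both, a true null would be reported as an increase more often than the nominal rate. For leptin, insulin and cortisol the documents predict no increase, and there the same bias makes a fall harder to detect.

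**Working it through.** **Inputs.**
- Completers: 40 enrolled with 15–25% drop-out (Protocol, Number of Local Participants), so 40 × 0.75 = 30 to 40 × 0.85 = 34.
- Level: the SAP states none for these tests. Assumed two-sided 0.05, that is 2.5% per side.
- Within-subject CV: not in the documents. Range shown: 0.1 to 0.5, equal in both sessions, errors independent.
- The plan gives no power, error rate or SD for these tests, so there is no figure to reproduce.

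**Hand example.** One subject eats 600 kcal (DS) and 300 kcal (NSD); another eats 300 and 600.
- Percentage change: +100% and −50%, mean +25%.
- Difference: +300 and −300 kcal, mean 0.
- Log ratio: ln 2 and −ln 2, mean 0.

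**General result.** Let R = DS/NSD. With no sleep effect and randomised order the two sessions are exchangeable, so R and 1/R have the same distribution. Then E[R] = E[(R + 1/R)/2] ≥ 1, with equality only if the sessions never differ. The mean percentage change is therefore above zero whatever the error distribution, for positive values.

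**Size of the bias.** For lognormal error with log-variance s² = ln(1 + CV²) in each session, ln R has variance 2s², so E[R] = exp(s²) = 1 + CV². The bias is 100 × CV² per cent. For gamma error it is 1/(k − 1) with k = 1/CV²; at CV 0.5, k = 4 and the bias is 1/3 = 33%.

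**Error rates under the null** (lognormal, 40,000 simulated trials per cell):

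| CV | Mean change | False increase, n = 30 / 34 | False decrease, n = 30 / 34 |
|---|---|---|---|
| 0.1 | +1% | 4.5% / 4.9% | 1.3% / 1.3% |
| 0.2 | +4% | 7.8% / 8.7% | 0.7% / 0.6% |
| 0.3 | +9% | 12.1% / 14.3% | 0.4% / 0.3% |
| 0.4 | +16% | 17.3% / 20.6% | 0.2% / 0.1% |
| 0.5 | +25% | 22.6% / 27.2% | 0.1% / 0.1% |

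Under the same null, the paired-difference and log-ratio tests stay at about 2.1–2.7% per side. Gamma error gives mean changes of +1, +4, +10, +19 and +33%, with false-increase rates of 5%, 8–9%, 13–15%, 18–22% and 25–29%. More subjects make it worse: at CV 0.3 the total two-sided error is 12.7% at n = 30, 14.4% at n = 34 and 17.5% at n = 40.

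**Label swap.** At n = 30, DS relative to NSD and NSD relative to DS both show a positive mean change in 29, 53, 70, 82 and 89% of null trials for CV 0.1 to 0.5. A paired difference or log ratio can never do this, because swapping the labels only reverses its sign.

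**Power.** For mirror-image true ratios of 1.2 and 1/1.2 (CV 0.3, n = 30), the SAP's test declares the increase in 89% of trials and the decrease in 30%. The log ratio gives 64–65% both ways.

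**Averaging of samples.** The protocol draws blood serially, "resulting in 5 samples, including a fasted baseline (6 pm"; the SAP does not say how a session value is formed. If the five ghrelin values are averaged, session CV = c × √(ρ + (1 − ρ)/5), where c is the single-sample CV and ρ the within-session correlation. With c = 0.3 and ρ = 0, 0.5 or 0.8, the session CV is 0.13, 0.23 or 0.28 and the bias +1.8%, +5.4% or +7.6%.

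**The case against.** The strongest reply concerns size, not direction. The documents give no within-subject CV. At CV 0.1 the bias is one percentage point and the false-increase rate under 5%; at CV 0.05 it is about 0.25% and 3.5%. Whether buffet calories or ghrelin lie higher cannot be read from the documents. That stands, and the size has to be stated as conditional.

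Other points also carry weight:
- The neural primary endpoint is untouched, because the SAP subtracts accuracy maps. The link to the primary endpoint runs through ghrelin alone, and averaging samples would shrink the bias there.
- Aim 1 says that orexigenic hormones will be altered, without a direction in that sentence. The expected rise comes from the surrounding background text.
- A one-sample test on within-subject change is still a paired analysis, so only the scaling departs from the protocol, and only for calorie intake.
- Zero intake at the NSD buffet is hypothetical: no such case is reported. The buffet does follow dinner, however, so small denominators are possible.
- If differences were divided by the group-mean NSD value, the t-statistic would equal that of the paired t-test and the problem would vanish. The SAP does not say this.

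None of these restores zero as the null mean of the per-subject percentage.

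**Conclusion.** The concern holds. Under the natural reading, the SAP's test for food intake and hormones has a positive null mean, and nothing else in the plan corrects it. This is mathematical and needs no outside figure. The size rests on an assumed CV, equal and independent errors, and 30–34 completers. It is minor at a CV of 0.1 or less and material from about 0.2, where the false-increase rate is roughly three times nominal (7.8–8.7% against 2.5%).

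The case for treating this as a required change rests on buffet calories, which may well be variable, and on ghrelin if its session CV is about 0.2 or more. Energy density is bounded by the snacks offered, so a large bias is less plausible there. The rule is wrong as written and cheap to replace.

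**What to change.** - **Buffet calories:** the protocol's paired t-test on the DS − NSD difference in kcal, with zero intake kept as 0.
- **Hormones:** define the session value, then a paired t-test of ln(DS) − ln(NSD), reported as a ratio of geometric means with 95% CI. This still reads as a percentage change.
- **Energy density:** paired difference in kcal/g among subjects who ate in both sessions, with the number excluded reported.
- **Per-subject percentage change:** descriptive only.

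The cost is SAP wording and a rerun of simple tests on data that, from the SAP's past tense, are already collected. The reported percentage increases may shrink, and the energy-density test loses anyone who ate nothing in a session. The kcal difference can also be less powerful than the log ratio if effects are multiplicative and subjects differ widely. With n = 30, CV 0.3 and a true ratio of 1.2, its power is 57%, 46–47% and 37–38% for between-subject CVs of 0.4, 0.8 and 1.2, against 64% for the log ratio. It remains valid, is the test the protocol planned, and handles zeros. If the sponsor prefers another symmetric test, the SAP should name it and say how zeros are treated.

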### **Analysis of hormones**

Ghrelin, leptin, insulin, and cortisol were measured in blood samples collected at each session. Changes in hormone levels in the deprived sleep (DS) session were computed as percentage change from non-sleep deprived baseline (NSD) and tested against zero using one-sample t-tests.

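### The SAP's hormone test does not say which of the five samples, or what summary of them, it uses, and its percentage-change t-test leans towards finding increases

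*SAP*

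**What the plan says.** The protocol's Primary endpoints section includes "levels of orexigenic hormones using the serial blood samples". Under Procedures Involved, Hormone levels, it states "We will draw blood every 30 min after arrival, resulting in 5 samples". The draws are at 6:00 (fasted), 6:30 (after dinner), 7:00, 7:30 and 8:00 pm, the last being taken "and after the scanning session (8 pm) for leptin and ghrelin analysis". Insulin appears only in the assay list ("until assay for ghrelin, leptin, insulin using commercially available ELISA kits"), with no number of time points. The endocannabinoids are sampled once: "An additional sample will be collected at 7:30 pm time point for 2-AG and 2-OG analysis". The protocol does not mention cortisol.

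The Background names ghrelin, 2-AG and 2-OG as orexigenic.

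The SAP's Analysis of hormones is two sentences. The first reads "Ghrelin, leptin, insulin, and cortisol were measured in blood samples collected at each session". The second gives one rule, a percentage change of the deprived session from the non-deprived one, tested against zero with one-sample t-tests. It covers neither 2-AG nor 2-OG.

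No other section fills the gap. The protocol's statistical text assigns paired t-tests to appetite ratings and calorie intake, and gives no test comparing hormone levels between conditions. The only multiplicity correction in the SAP is for the fMRI maps.

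**The concern.** The SAP rule needs one number per person per session, and the endpoint supplies five. The draws run from fasted to fed, so they are not interchangeable, and the choice of draw or summary changes the hypothesis being tested. With that choice open, a claim on a primary endpoint could rest on whichever ghrelin sample turned out significant.

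The stated rule has a second weakness that does not depend on which sample is used. A ratio of two noisy measurements averages above 1 even when nothing has changed. Testing mean percentage change against zero therefore favours an increase, which for ghrelin is the direction the protocol expects.

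**Working it through.** **Inputs from the documents.** Draws every 30 minutes from 6 to 8 pm: 120/30 + 1 = 5, which matches the protocol's count. Enrolment is 40 with 15-25% drop-out, leaving 40 × 0.85 = 34 to 40 × 0.75 = 30 completers; I use n = 32.

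**Assumptions.** The documents give no alpha for hormones, so I take 5% two-sided per test. They give no correlations or SDs, so ranges are shown.

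**1. Family-wise error if every draw is tested.** For k independent tests it is 1 − 0.95^k. For correlated draws I simulated one-sample t-tests at n = 32, with equal correlation ρ among a hormone's five draws and independence between hormones.

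| Family | Tests | Independent | ρ = 0.5 | ρ = 0.7 | ρ = 0.9 |
|---|---|---|---|---|---|
| Ghrelin | 5 | 22.6% | 18% | 15% | 10% |
| Ghrelin and leptin | 10 | 40.1% | 34% | 28% | 19% |

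With one summary for each of the SAP's four hormones, the figure is 1 − 0.95^4 = 18.5% if independent and uncorrected. With one ghrelin test it is 5%.

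**2. Bias of percentage change under no effect.** Let s be the within-subject SD of log concentration in one session, independent between sessions. The log ratio then has variance 2s², and the expected percentage change is exp(s²) − 1.
- s = 0.2: exp(0.04) − 1 = 4.1%
- s = 0.3: exp(0.09) − 1 = 9.4%

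Simulating the SAP's t-test at n = 32 with no true change gives rejection rates of about 9% (s = 0.2) and 14% (s = 0.3), nearly all as increases. The same test on log differences rejects 5% of the time.

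**3. Does averaging the draws cure the bias?** Averaging five log values multiplies s² by (1 + 4ρ)/5, which is 0.76 at ρ = 0.7. The bias becomes exp(0.0304) − 1 = 3.1% or exp(0.0684) − 1 = 7.1%. Most of it remains, so the change of scale is what removes it.

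**4. Power of the summary.** Take an effect of 0.4 SD per sample at n = 32. One draw gives 59% power. The five-draw mean has standardised effect 0.4/√0.76 = 0.46 at ρ = 0.7 and 0.4/√0.6 = 0.52 at ρ = 0.5, giving 71% and 81%. This assumes the same effect at all five times. If it is present at only four, power at ρ = 0.7 is 52%; at three, 33%.

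**The case against.** A reader might multiply four hormones by five draws and conclude that the primary claim rests on any of 20 uncorrected tests, with a family-wise error of 1 − 0.95^20 = 64%. The documents do not support that. Five draws are explicit only for ghrelin and leptin; the number of insulin and cortisol time points is not stated. Leptin, insulin and cortisol are not called orexigenic, so at most five of the 20 tests bear on the primary endpoint.

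Nor can silence be read as conduct. The SAP states no correction, but it does not say that none was applied or that single draws were tested. Its rule may well have been used with one value per session.

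It is also fair to say that a five-draw mean is not automatically better. It loses power if the effect is confined to a few times around the meal, as step 4 shows. And making ghrelin the only primary hormone without comment would drop 2-AG and 2-OG from an endpoint the protocol words in the plural.

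All of this narrows the point and shapes the remedy. It does not supply the missing summary, and it does not answer the upward bias of the stated test.

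**Conclusion.** The point holds in limited form and should be acted on. The analysis variable for a serially sampled primary endpoint is undefined, and no multiplicity rule is stated for it. For ghrelin the exposure is a family-wise error of up to 23%, or about 10% to 18% at assumed correlations of 0.9 to 0.5. For ghrelin and leptin together it is up to 40%. Twenty tests is an upper bound that the documents do not establish.

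The percentage-change test is a separate defect in what the SAP does state: a true null is rejected about 9% to 14% of the time at n = 32 if the within-subject log-SD is 0.2 to 0.3. The error rates rest on the assumed 5% level, correlations and SDs. The missing summary rests on the text alone.

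**What to change.** Replace the rule in the SAP's Analysis of hormones as follows.

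- For each serially sampled hormone, compute one summary per session: the time-weighted mean of log concentration over the scheduled samples. With five draws at equal spacing, trapezoid weights are 1/8, 1/4, 1/4, 1/4, 1/8.
- Test the within-subject difference (deprived minus non-deprived) in that summary once, and back-transform it to a percentage change for reporting.
- Name this single contrast. Do not offer a mixed model with condition, time, their interaction and order as an alternative: its condition effect depends on coding and it is not the same test.
- Make ghrelin the primary serial-hormone test. For 2-AG and 2-OG (one 7:30 pm sample each), use the log difference, and either keep them with ghrelin in the primary family under Holm or explicitly reclassify them.
- Treat leptin, insulin and cortisol as secondary, and state at which draws insulin and cortisol were assayed.
- Report individual time points descriptively.

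The SAP is written in the past tense, so date the change and report any percentage-change result already run beside the new one.

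The cost is a few lines of SAP text and minor programming, with no new data. The price is no inferential claim at single time points, and some loss of power if the effect is confined to a few draws.
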